1 BACKGROUND AND RATIONALE

the *Journal of the American Statistical Association* (1955, 50, 355-372) and the *Journal of the Royal Statistical Society, Series B* (1956, 21, 204-215). The first paper is a general introduction to the theory of quadratic forms in normal variables, and the second is a detailed treatment of the theory of quadratic forms in quadratic normal variables. The theory of quadratic forms in quadratic normal variables is a generalization of the theory of quadratic forms in normal variables, and it is used in the analysis of variance of quadratic forms in quadratic normal variables. The theory of quadratic forms in quadratic normal variables is also used in the analysis of variance of quadratic forms in quadratic normal variables.

Research Hypothesis:

Combination therapy with DCV and SOF plus RBV for 24 weeks is safe and demonstrates an SVR12 rate greater than the threshold SVR rate in chronically infected subjects with HCV GT-3 and cirrhosis.

Schedule of Analyses:

- The analysis for the primary endpoint will be performed after all subjects have reached post-treatment Week 12 (SVR12) ;
- The final analysis (SVR24) will be performed at study completion.

[figure not shown]
2 STUDY DESCRIPTION

2.1 Study Design

Study design schematic is presented in Figure 2.1-1.

Figure 2.1-1: Study Design Schematic

Subjects with GT-3 Infection with Cirrhosis

AI444379 is an open label, one-arm trial evaluating the combination therapy of DCV and SOF plus RBV for 24 weeks duration in GT-3 subjects with cirrhosis.

Subjects will receive the combination of DCV 60 mg QD (unless concomitant HIV regimen dictates otherwise) + SOF 400 mg QD + RBV (weight based 1000 mg-1200 mg daily) for 24 weeks.

As an open label study, HCV RNA will be available for review by the clinical site personnel. Any subject who discontinues therapy before the protocol-defined treatment duration should have 24 weeks of post-treatment follow-up. The screening/enrollment period is anticipated to be approximately 8 weeks from FPFV to LPFV. Study duration will be 52 weeks (4 week screening period, 24 weeks of therapy, and 24 weeks of follow-up).

Any subject who receives anti-HCV therapy in the post-treatment period prior to Week 4 (i.e., a subject who discontinued therapy due to an AE or virologic failure who then chooses to receive an alternative therapy outside of the study), should discontinue from the study after completing the post-treatment Week 4 safety visit. If the subject receives HCV therapy after post treatment Week 4, the subject should be discontinued from the study as soon as possible, following completion of the procedures outlined in the Post-treatment Week 24 visit.

The end of the study is defined as the date of the last visit for the last subject to complete the study. The last visit is defined as the last post-treatment follow up subject visit.

2.2 Treatment Assignment

2.3 Blinding and Unblinding

This is an open label study.

2.4 Protocol Amendments

N/A.

3 OBJECTIVES

3.1 Primary

- To demonstrate the SVR12 rate, defined as HCV RNA < LLOQ target detected (TD) or target not detected (TND) at follow-up Week 12 in subjects treated with 24 weeks of DCV+SOF+RBV therapy is greater than the historical threshold SVR rate.

3.2 Key Secondary

- To assess the impact of baseline NS5A resistance-associated polymorphisms on the SVR12 rate.

3.3 Secondary

- To assess safety, as measured by the frequency of deaths, serious adverse events (SAEs), discontinuation due to adverse events (AE)s, Grade 3/4 AEs and Grade 3/4 lab abnormalities observed from clinical laboratory testing.
- To assess antiviral activity, as measured by
 - The proportion of subjects who achieve HCV RNA < LLOQ-TD or TND at each of the following Weeks: 1, 2, 4, 8, 12, 16, 20, 24, and EOT; post-treatment Weeks 4 and 24.
 - The proportion of subjects who achieve HCV RNA < LLOQ TND at each of the following Weeks: 1, 2, 4, 8, 12, 16, 20, 24, and EOT.

3.4 Exploratory

4 ENDPOINTS

Efficacy analyses will evaluate HCV RNA as measured by the Roche COBAS® AmpliPrep/COBAS® TaqMan® HCV Test [lower limit of quantification (LLOQ): 15 IU/mL].

4.1 Primary Endpoints

Proportion of subjects with SVR12, defined as HCV RNA < LLOQ, target detected (TD) or target not detected (TND) at follow-up Week 12 in all treated subjects. Missing HCV RNA data at follow-up Week 12 will be imputed using the Next Value Carried Backwards (NVCB) approach, i.e., missing HCV RNA data in the follow-up Week 12 window will be imputed using the next and closest available HCV RNA measurement after the follow-up Week 12 HCV RNA window.

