3.4.5 Other Restrictions and Precautions

- Medications with known or potential anti-HCV activity other than the assigned study treatment are prohibited during the on treatment period
- Any prescription or herbal product which is not prescribed by the investigator or licensed physician for treatment of a specific clinical condition is prohibited
- Methadone and buprenorphine should be used with caution. These drug levels may change with concomitant use of DCV and SOF
- Long-term treatment (\geq 2 weeks) with agents that are immunosuppressive, or have a high risk for nephrotoxicity or hepatotoxicity, should be discussed with the central medical monitor

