3.5 Discontinuation of Subjects following any Treatment with Study Drug

Subjects MUST discontinue investigational product (and non-investigational product at the discretion of the investigator) for any of the following reasons:

- Subject's request to stop study treatment
- Any clinical adverse event (AE), laboratory abnormality or intercurrent illness which, in the opinion of the investigator, indicates that continued participation in the study is not in the best interest of the subject
- Termination of the study by Bristol-Myers Squibb (BMS)

- Loss of ability to freely provide consent through imprisonment or involuntarily incarceration for treatment of either a psychiatric or physical (eg, infectious disease) illness
- Pregnancy
- Laboratory or Clinical Criteria: If any of the following laboratory or clinical criteria is obtained for any patient, the result must be repeated /confirmed within 72 hours and the BMS central medical monitor should be informed. If the results are confirmed, the patient must discontinue treatment. Clinical criteria must have Principal Investigator or Sub-Investigator assessment prior to proceeding to permanent discontinuation
 - Evidence of confirmed hepatic decompensation (Child-Pugh Class B or C, Score > 6)
 - ALT > 2 × baseline and 5 × ULN, and either total bilirubin > 2 × ULN or INR > 2
 - Any Grade 4 AE or clinically significant laboratory abnormality considered study drug-related (see [Section 6.3](#) for laboratory abnormality AE reporting requirements).
- Virologic Breakthrough (confirmatory results must be obtained 2 weeks from the original result) defined as:
 - Confirmed $\geq 1 \log_{10}$ IU/mL HCV RNA on-treatment increase from nadir, or
 - Confirmed increase in HCV RNA \geq LLOQ if HCV RNA previously declined to < LLOQ TD/TND.

If discontinuation of therapy is required, this must occur no later than the next study visit.

Any subject who receives anti-HCV therapy in the post-treatment period prior to Post-Treatment Week 4 (ie, a subject who discontinued therapy due to an AE or virologic failure), who then chooses to receive an alternative therapy (outside of the study), should discontinue from the study after completing the Post-Treatment Week 4 safety visit (see [Table 5.1-3](#)). If the subject receives HCV therapy after Post-Treatment Week 4, the subject should be discontinued from the study as soon as possible, following completion of the procedures outlined in the Post-Treatment Week 24 visit.

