5.4.2 Secondary Efficacy Assessments

HCV RNA collected at each of the following Weeks: 1, 2, 4, 8, 12, 16, 20 and 24 (EOT); post-treatment Weeks 4 and 24 will be used for the secondary antiviral assessment in this study.

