8.4.2 Efficacy Analyses

Efficacy endpoints during the on-treatment period will be based on HCV RNA measurements closest to the planned visits within pre-defined visit windows. Efficacy endpoints during the follow-up period will be based on the last HCV RNA measurements in pre-defined visit windows.

The primary analysis for the proportions of patients meeting the efficacy endpoints will be for all treated subjects.

For binary efficacy endpoints including secondary efficacy endpoints, response rates and 2-sided 95% exact Binomial confidence intervals (CIs) will be estimated for each treatment arm.

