8 CONVENTIONS

8.1 Visit Definition

Visits are defined below. Subjects receive up to 24 weeks of study therapy and are followed for an additional 24 weeks. Windows are constructed for each visit in order to slot data. Labels for study periods and visits appear in listings and datasets.

Table 8.1-1: Visit Definition

Study Period Label	Visit Label	Visit Number	Target Day from Start of Study Period	Visit Window
PRE-TREAT	PRE-TREAT	1	1	< 1 day ^a
ON-TREAT	DAY 1	2	1	1 - 4 days
	WEEK 1	3	7	5 days - 11 days
	WEEK 2	4	14	12 days - 3 weeks
	WEEK 4	5	28	> 3 weeks - 6 weeks
	WEEK 8	6	56	> 6 - 10 weeks
	WEEK 12	7	84	> 10 - 14 weeks
	WEEK 16	8	112	> 14 - 18 weeks
	WEEK 20	9	140	> 18 - 22 weeks
	WEEK 24	10	168	> 22 weeks
FOLLOW-UP	F/U WEEK 4	11	21	> 1 - 8 weeks

[figure not shown]
Table 8.1-1: Visit Definition

Study Period Label	Visit Label	Visit Number	Target Day from Start of Study Period	Visit Window
	F/U WEEK 12	12	77	> 8 - 18 weeks
	F/U WEEK 24	13	161	> 18 weeks

^a See [Section 6.1](#), Study Periods, for classification of measurements on Day 1 (first dose of active study therapy) as pre-treatment or on-treatment depending on the data domain.

For the definitions of time measurement, windows around planned measurement times, and study day/week, refer to the Core SAP Section 8.1.

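### The printed SVR12 rules do not exclude HCV RNA taken after non-study anti-HCV therapy starts, so a re-treated failure can count as a responder

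*SAP*

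**What the plan says.** SAP 4.1 (and Protocol 8.3.1 in the same terms) gives the primary endpoint as the proportion with SVR12, "defined as HCV RNA < LLOQ, target detected (TD) or target not detected (TND) at follow-up Week 12 in all treated subjects". If the Week 12 value is missing, it "will be imputed using the next and closest available HCV RNA measurement after the follow-up Week 12 HCV RNA window".

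Which sample counts as Week 12 is set in two places. Protocol 8.4.2 states: "Efficacy endpoints during the follow-up period will be based on the last HCV RNA measurements in pre-defined visit windows". SAP Table 8.1-1 sets the follow-up Week 12 window at > 8 to 18 weeks, and everything after 18 weeks belongs to follow-up Week 24.

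Other anti-HCV drugs are banned only while study drug is being taken (Protocol 3.4.5): "Medications with known or potential anti-HCV activity other than the assigned study treatment are prohibited during the on treatment period". For later use, Protocol 3.5 says: "If the subject receives HCV therapy after Post-Treatment Week 4, the subject should be discontinued from the study as soon as possible", and it attaches a condition that SAP 2.1 repeats: "following completion of the procedures outlined in the Post-treatment Week 24 visit". HCV RNA is an efficacy sample at that visit (Protocol 5.4.2): "post-treatment Weeks 4 and 24 will be used for the secondary antiviral assessment in this study". A subject who starts other therapy before post-treatment Week 4 leaves after the Week 4 safety visit.

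**The concern.** The exit rule produces an HCV RNA sample after a new regimen has begun, and the endpoint rules accept that sample without condition. Breakthrough and relapse are defined in the protocol (3.1 and 3.5), but nothing visible ties either to SVR12 status. Sites see HCV RNA results, so a failure is known and can be re-treated.

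The bias runs one way. Another regimen can make a failure look like a response, and in practice it will not do the reverse. The subjects affected are the failures that the trial exists to count, and the conclusion depends on one lower confidence bound in 75 subjects.

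**Working it through.** **Tracing the rules.** Times are weeks after the end of treatment.

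| Course | Primary (NVCB) | mITT | Observed values |
|---|---|---|---|
| RNA ≥ LLOQ at Week 12, new regimen at Week 13, exit sample < LLOQ at Week 17 (last in window) | Responder | Responder | Responder |
| No sample in > 8 to 18 weeks, new regimen after Week 4, exit sample < LLOQ after Week 18 | Responder, carried back | Non-responder | Dropped |
| RNA ≥ LLOQ at Week 12, exit sample after Week 18 | Non-responder | Non-responder | Non-responder |
| New regimen before Week 4, leaves after that visit | Not affected | Not affected | Not affected |
| Exit sample by Week 8, none later | Not affected | Not affected | Not affected |

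In the first row the value is observed, so neither sensitivity analysis in SAP 7.5.1 reveals the problem. In the second row the mITT analysis does.

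**Inputs.** n = 75 and threshold 79% (Protocol synopsis, Sample Size); exact binomial two-sided 95% interval, with success if the lower bound exceeds 79% (SAP 7.5 and 7.5.1).

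**The plan's own figure.** The exact lower bound for x responders is the 0.025 quantile of Beta(x, 75 − x + 1). For 68/75 the interval is 81.71% to 96.16%, which matches the printed 81.7% to 96.2%.

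**Effect of one subject.** Each adds 1/75 = 1.33 percentage points.

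| Responders | Lower bound | Exceeds 79%? |
|---|---|---|
| 66 | 78.44% | No |
| 67 | 80.06% | Yes |
| 68 | 81.71% | Yes |

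The exact rule is therefore met from 67, although the protocol gives 68 as the minimum. Both cut-offs are shown below. From 66, one misclassified subject reaches 67 and two reach 68.

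**Chance of success when the true rate is 79%.** The documents give no re-treatment rate, so the rows are assumptions. For a fixed number m of misclassified subjects the chance is P(X ≥ c − m), with X binomial(75, 0.79) and c the cut-off. For a share q of failures misclassified, the apparent rate is 0.79 + 0.21q and the chance is P(X ≥ c) at that rate.

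| Assumption | c = 67 | c = 68 |
|---|---|---|
| None | 1.5% | 0.6% |
| m = 1 | 3.2% | 1.5% |
| m = 2 | 6.3% | 3.2% |
| q = 5% (rate 80.05%) | 2.5% | 1.1% |
| q = 10% (rate 81.1%) | 4.1% | 1.8% |
| q = 20% (rate 83.2%) | 9.8% | 5.0% |

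**Break-even.** The chance reaches the nominal one-sided 2.5% at q = 5.05% (c = 67) or 12.9% (c = 68). Expected failures at 79% are 75 × 0.21 = 15.75, so these shares are 0.0505 × 15.75 ≈ 0.8 and 0.129 × 15.75 ≈ 2.0 subjects.

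**The case against.** The strongest objection is that the absence of a rule cannot be proved from these documents. SAP 6.1 and 7.1 defer to the Core SAP, SAP 8.1 does the same ("For the definitions of time measurement, windows around planned measurement times, and study day/week, refer to the Core SAP Section 8.1"), and SAP 8.2 on domain derivations shows no text here, perhaps through redaction. An exclusion could sit in either place. This stands as a limit. However, SAP 4.1 and 7.5.1 set out the primary rule in detail without pointing to any exclusion, so a citation is needed even if one exists.

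The protocol also assigns the Week 12 sample to the primary assessment (5.4.1) and the Week 24 sample to the secondary (5.4.2), so an exit visit run as Week 24 might be read as secondary only. The windows in Table 8.1-1 go by time, however, and would still place an exit sample at, say, Week 17 in Week 12.

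The in-window route is narrow. Office visits fall at Weeks 4, 12 and 24, with telephone contacts between (Protocol 5.8.3). A relapse found at Week 12 must be confirmed, re-treated, suppressed below 15 IU/mL and sampled by Week 18, while exit is to be prompt. The carried-back route needs an empty ten-week window, and the mITT analysis corrects it. Many failures could not follow either route. All this bears on frequency, and it stands: at a cut-off of 68, one misclassified subject or 10% of failures leaves the error under 2.5%. It does not change how such a subject is scored.

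Finally, that the exit visit includes HCV RNA rests on Protocol 5.4.2, because the visit table is not in the text.

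**Conclusion.** The concern holds for the rules as printed. They would score a failure suppressed by another regimen as an SVR12 responder, and for in-window samples no planned analysis would show it. The number of subjects is likely to be small and cannot be estimated from the documents, but one can change the conclusion at the exact cut-off of 67, and two at the protocol's stated 68. Type I error stays within 2.5% unless more than about 5% (cut-off 67) or 13% (cut-off 68) of failures are misclassified. The conclusion assumes that the exit visit includes HCV RNA and that no exclusion sits in the Core SAP or SAP 8.2, so confidence is moderate. It should be fixed.

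**What to change.** Add the following to SAP 4.1 and 7.5.1 and Protocol 8.3.1 and 8.4.2.1:

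> HCV RNA measured after the start of any non-study anti-HCV therapy is not used, either as an observed follow-up value or for NVCB. In the primary and mITT analyses, the last in-window value taken before that therapy started decides SVR12 status. If the window holds no such value, the subject is a non-responder, except that the primary analysis may carry back a later value taken before that therapy started. In the observed-value analysis, a value taken after that therapy started is treated as not observed, and an earlier in-window value is kept.

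Apply the same exclusion to SVR24. If the Core SAP already has this rule, cite it in SAP 4.1 and 7.5.1 instead. The exit rules need no change.

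The cost is a short rule and a date filter on concomitant medication, or one cross-reference. The filter needs start dates of anti-HCV therapy during follow-up. The visible text does not show that these are collected, so the sponsor should confirm it. The reported SVR12 rate may be slightly lower.

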4.2 Key Secondary Endpoints

The proportion of subjects who achieve SVR12 in the presence and absence of baseline NS5A resistance-associated polymorphisms.

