1.3.2 Key Secondary Objective

- To assess the relationship between efficacy and NS5A resistance-associated polymorphisms.

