3.1 Study Design and Duration

The study design schematic is presented in [Figure 3.1-1](#).

Figure 3.1-1: Subjects with GT-3 Infection with Cirrhosis

Study Design

Subjects with GT-3 Infection with Cirrhosis

AI444379 is an open-label trial evaluating the combination therapy of DCV + SOF with RBV for 24 weeks in subjects infected with HCV GT-3 with compensated cirrhosis. Subjects with cirrhosis who are mono-infected with HCV genotype 3 or coinfecte^d with HCV genotype 3 and HIV-1 infection will be permitted to enroll. The study will include approximately 75 subjects.

Subjects will receive the combination of DCV 60 mg QD (unless otherwise dictated by concomitant combination anti-retroviral therapy [cART] therapy) + SOF 400 mg QD + RBV (weight based 1000 mg-1200 mg daily) for 24 weeks. HCV RNA will be available for review by the clinical site personnel. After treatment is completed, subjects will be followed for 24 weeks. Subjects who discontinue early should be followed for 24 weeks post-treatment.

The primary analysis is SVR12 and the final analysis is SVR24.

Duration of study:

The screening/enrollment period is anticipated to be approximately 8 weeks from FPFV to LPFV. Study duration will be 52 weeks (4 week screening period, 24 weeks of therapy, and 24 weeks of follow-up).

Virologic Failure:

Virologic breakthrough is defined as:

1. Any confirmed ≥ 1 log₁₀ increase in HCV RNA from nadir, OR;
2. Any confirmed HCV RNA \geq LLOQ after HCV RNA $<$ LLOQ, TD or TND while on treatment

Subjects who meet a definition of viral breakthrough will discontinue therapy. If discontinuation of therapy is required, this must occur no later than the next study visit following confirmation of breakthrough.

Viral relapse is defined as:

Confirmed HCV RNA \geq LLOQ in post-treatment follow-up after HCV RNA $<$ LLOQ, TND at EOT

Long-term follow-up study: Following completion of the follow-up period of the study, select subjects at selected sites may be asked to enroll into a separate long term observational 3 year follow-up study to evaluate durability of response (if SVR is achieved) or persistence of possible drug-resistant virus (if treatment failure occurs). It is not a requirement for all subjects to enroll into the long term follow-up, and this option may not be available.

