7.1 General Methods

Laboratory abnormalities are determined from laboratory measurements analyzed at the central or local laboratory.

Otherwise, refer to Core SAP Section 7.1.

There is only one treatment regimen in this study. Analyses are planned to be presented for all treated subjects by prior HCV therapy status (naive, experienced), coinfection status (HCV monoinfected, HCV/HIV coinfecte) and overall. Depending on enrollment, if only a minimum number of HCV/HIV coinfecte subjects are enrolled, Analyses will be presented by prior HCV therapy status (naive, experienced) and overall.

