7.3.2.2 Baseline Disease Characteristics and Prognostic Factors

All subjects in this study are GT-3 Infected with cirrhosis.

Otherwise, refer to Core SAP Section 7.3.2.2.

7.3.2.3 *Other Baseline Characteristics*

Refer to Core SAP Section 7.3.2.3.

7.4 *Extent of Exposure*

Study therapy of this study is DCV+SOF+RBV.

Refer to Core SAP Section 7.4. In addition, proportions of subjects with RBV dose reduction, and RBV discontinuation will be presented separately. RBV discontinuation will be defined as last RBV dosing date < last treatment dosing date -1. Time to the first RBV dose reduction and time to RBV discontinuation will also be summarized.

Subjects with full RBV dosing, dose reduction or interruptions > 14 days are summarized. A subject listing is generated for all subjects who received a full RBV dose or experienced a reduction or interruption in RBV dose. This listing will include time on study therapy, treatment start and stop dates, weight, target daily dose, total daily dose received, reason for modification, duration adherence, and dose adherence.

7.5 *Efficacy*

For binary efficacy endpoints, 2-sided 95% CIs will be calculated based on exact binomial distribution.

7.5.1 *Primary Efficacy Endpoint*

The primary analysis will be performed after all subjects have reached post-treatment Week 12 (SVR12). A final analysis (SVR24) will be performed at study completion.

The primary analysis for the primary endpoint SVR12 will be computed on all treated subjects, and missing HCV RNA data at follow-up Week 12 will be imputed using the Next Value Carried Backwards (NVCB) approach, ie, missing HCV RNA data in the follow-up Week 12 window

will be imputed using the next and closest available HCV RNA measurement after the follow-up Week 12 HCV RNA visit window.

The lower bound of the SVR12 95% confidence interval (CI) will be used to compare to the historical threshold of 79%. If it exceeds 79%, it can be concluded that the primary objective is achieved.

The following sensitivity analyses on the primary endpoint will also be conducted:

- Sensitivity analysis using mITT (Missing=Non-Responder): SVR12 rates and two-sided 95% CIs will use all treated subjects. The SVR12 status for subjects with missing follow-up Week 12 HCV RNA will be counted as non-responders.

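### The key secondary objective asks for the impact of baseline NS5A polymorphisms on SVR12, but the visible text plans only two separate rates with exact CIs; confirm that a difference with its own CI is specified, or add one

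*SAP*

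**What the plan says.** The SAP states the key secondary objective in section 3.2 as "To assess the impact of baseline NS5A resistance-associated polymorphisms on the SVR12 rate". Protocol 1.3.2 words it as "To assess the relationship between efficacy and NS5A resistance-associated polymorphisms". Both set one group against another.

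The endpoint in SAP 4.2, and in the same terms in Protocol 8.3.2, is a pair of proportions: "The proportion of subjects who achieve SVR12 in the presence and absence of baseline NS5A resistance-associated polymorphisms".

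Two general rules on method are visible. Protocol 8.4.2 says that for binary efficacy endpoints, secondary ones included, "response rates and 2-sided 95% exact Binomial confidence intervals (CIs) will be estimated for each treatment arm". SAP 7.5 says: "For binary efficacy endpoints, 2-sided 95% CIs will be calculated based on exact binomial distribution".

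Other places where a contrast might have been set out do not show one:
- SAP 7.1 lists the presentation groups as prior therapy, coinfection status and overall. NS5A status is not among them.
- Protocol 8.4.2.2 lists the secondary efficacy summaries without the key secondary endpoint.
- Protocol 8.4.8 covers how often substitutions occur, not SVR12 by baseline polymorphism.
- SAP 7.5.2.5, on efficacy in subgroups, is a heading without body text in the public copy, and much of SAP section 7 defers to a Core SAP that is not supplied.

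**The concern.** An impact on SVR12 is a contrast between carriers and non-carriers, so its natural estimate is a difference (or ratio) with an interval of its own. The visible endpoint and methods give an interval for each rate and none for the contrast. A reader of the report could subtract the two rates but would not know how precise the result is.

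The obvious substitute is to lay the two intervals side by side, which is a poor guide. Two 95% intervals can overlap when the interval for the difference excludes zero, and exact intervals from a small group are wide. If the carrier group is small, a polymorphism that clearly lowers SVR12 could look inconclusive, and the trial's only key secondary question would lack a quantified answer.

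**Working it through.** **Inputs.** N = 75 (Protocol 3.1: "The study will include approximately 75 subjects"). Overall result 68/75 = 91% (SAP Table 5.1-1). Interval method: exact binomial, two-sided 95%. The visible text gives neither the number of carriers nor the SVR12 rate in each group, so both are assumptions below. Carriers range from 8 to 23 of 75 (11% to 31%).

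**Step 1: reproduce the plan's figure.** The Clopper-Pearson limits for x of n are the 2.5% quantile of Beta(x, n − x + 1) and the 97.5% quantile of Beta(x + 1, n − x). For 68/75 they are 81.71% and 96.16%, matching the SAP's 81.7% and 96.2%. The other five rows of the table also reproduce to rounding.

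**Step 2: split the 68 responders.** Assume 15 carriers with 11 responders, leaving 60 non-carriers with 57.
- Present: 11/15 = 73.3%, exact CI 44.9% to 92.2%.
- Absent: 57/60 = 95.0%, exact CI 86.1% to 99.0%.
- The intervals overlap from 86.1% to 92.2%.

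**Step 3: interval for the difference.** Newcombe's method uses the Wilson limits (l, u) of each rate, with d = p_absent − p_present:
- lower = d − √[(p_absent − l_absent)² + (u_present − p_present)²]
- upper = d + √[(u_absent − p_absent)² + (p_present − l_present)²]

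The Wilson limits are 0.8630 to 0.9829 (absent) and 0.4805 to 0.8910 (present), and d = 0.9500 − 0.7333 = 0.2167.
- lower = 0.2167 − √(0.0870² + 0.1577²) = 0.2167 − 0.1801 = 0.037
- upper = 0.2167 + √(0.0329² + 0.2528²) = 0.2167 + 0.2550 = 0.472

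The difference is 21.7 points (95% CI 3.7 to 47.2), with Fisher exact p = 0.026.

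**Step 4: other splits of 68/75.** The exact CIs overlap in every row.

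| Present | Absent | Difference, points (Newcombe 95% CI) | Fisher p |
|---|---|---|---|
| 5/8 (24.5% to 91.5%) | 63/67 (85.4% to 98.3%) | 31.5 (6.3 to 63.7) | 0.023 |
| 6/10 (26.2% to 87.8%) | 62/65 (87.1% to 99.0%) | 35.4 (10.8 to 64.3) | 0.005 |
| 11/15 (44.9% to 92.2%) | 57/60 (86.1% to 99.0%) | 21.7 (3.7 to 47.2) | 0.026 |
| 18/23 (56.3% to 92.5%) | 50/52 (86.8% to 99.5%) | 17.9 (2.8 to 38.2) | 0.025 |

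**Step 5: how often the two readings part.** I summed the two binomial distributions exactly over all outcomes, for assumed true rates (present vs absent). Entries are the percentage of trials.

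| Carriers | True rates | Exact CIs do not overlap | Newcombe CI excludes 0 | Fisher p ≤ 0.05 |
|---|---|---|---|---|
| 8 | 70% vs 94% | 16.4 | 56.5 | 41.9 |
| 11 | 70% vs 94% | 22.5 | 61.7 | 54.4 |
| 15 | 70% vs 94% | 29.6 | 68.6 | 64.7 |
| 23 | 70% vs 94% | 33.9 | 78.7 | 71.2 |
| 8 | 60% vs 95% | 39.0 | 80.1 | 68.2 |
| 11 | 60% vs 95% | 51.4 | 85.6 | 81.0 |
| 15 | 60% vs 95% | 63.8 | 91.2 | 89.4 |
| 23 | 60% vs 95% | 73.3 | 96.5 | 94.2 |

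**Step 6: false positives.** With a common true rate of 91% and 6 to 23 carriers, the Newcombe interval wrongly excludes zero in about 2.9% to 4.9% of trials, and the exact CIs fail to overlap in about 0.1%. The gain in step 5 does not come from exceeding the nominal 5%.

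**The case against.** The strongest objection is that the absence cannot be proved. SAP 7.5.2.5 is where a comparison by NS5A status would most naturally sit. Its body is not in the public copy, and the Core SAP is not available. No visible part of SAP section 7 analyses the key secondary endpoint at all, which points to text held elsewhere as much as to a plan that stops at two intervals. The general rules in Protocol 8.4.2 and SAP 7.5 also say how an interval for a rate is built; neither excludes a contrast specified in another place. This stands, and it turns the point into a request to confirm first.

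A reader might also infer that impact will be judged by whether the two intervals overlap. The documents do not say so. Only the primary endpoint has a decision rule (Protocol 8.4.2.1, SAP 7.5.1). Step 5 therefore shows what an informal side-by-side reading would miss, not how a planned test performs. Such a reading would be very conservative rather than prone to false claims.

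The harm is also limited. Both rates would be reported, and 73% against 95% would hardly pass as no effect. The point difference follows by subtraction, so what is missing is its interval. Finally, the carrier counts and true rates are assumed, and the effects in step 5 are large (24 and 35 points).

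None of this supplies a measure of uncertainty for the impact that the objective names.

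**Conclusion.** The point holds for the visible text: the objective is comparative, the endpoint is two proportions, and the stated interval method covers each rate alone. A flat statement that the plan contains no between-group difference would go too far, because SAP 7.5.2.5 and the Core SAP cannot be read.

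If no contrast is specified there, the key secondary question would be reported without an interval of its own. In the assumed splits of the 68/75 scenario, overlapping exact intervals coexist with differences of about 18 to 35 points whose 95% CIs exclude zero. With 8 to 23 carriers and true rates of 70% against 94%, non-overlap occurs in 16% to 34% of trials, whereas a Newcombe interval excludes zero in 57% to 79%. These sizes depend on the assumed carrier counts and rates; the mismatch between objective and visible method does not.

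This is a worthwhile clarification of a descriptive analysis. It does not affect the primary conclusion.

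**What to change.** First check whether SAP 7.5.2.5 or the Core SAP already specifies an SVR12 difference by baseline NS5A status with a 95% CI. If so, a cross-reference from SAP 4.2 is enough.

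If not, keep the two rates with their exact CIs and add to the key secondary analysis the difference in SVR12, polymorphism absent minus present, with a two-sided 95% score CI (Miettinen-Nurminen or Newcombe, named in advance). State that this is the descriptive estimate for the key secondary objective and carries no multiplicity claim.

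The cost is one sentence in the SAP and one table row, with no new data, subjects or alpha. The downside is a wide interval when carriers are few: from 63.7 − 6.3 = 57.4 points with 8 carriers to 38.2 − 2.8 = 35.4 points with 23 in the examples. That width tells the reader how much the carrier group can support.
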